#### 5.2.2 Specify inclusion/exclusion criteria for cohort entry and define the index date.

Inclusion and exclusion criteria were adapted from the trial as closely as possible. Definitions for all inclusion/exclusion are provided in **Appendix A** and are summarized in the flowcharts below.

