| Excluded based on Inclusion # 3b - Acute Symptomatic PE and based on Inclusion # 4 - Age                                                                                                                                                                                                                                                      | -4,641   | 8,593   | -2852    | 8,382   | -21,229    | 20,793    |
| Excluded based on Exclusion # 1 - pregnancy                                                                                                                                                                                                                                                                                                   | -14      | 8,579   | -42      | 8,340   | -22        | 20,771    |
| Excluded based on Exclusion # 6 - Thrombectomy, Insertion of Caval Filter, or Use of Fibrinolytic Agent                                                                                                                                                                                                                                       | -211     | 8,368   | -143     | 8,197   | -24        | 20,747    |
| Excluded based on Exclusion # 7 - Active bleeding (HAS_BLED Score >=3), based on Exclusion # 10A - Mechanical Valve, and based on Exclusion # 11.1 - Intracranial Bleeding                                                                                                                                                                    | -3,708   | 4,660   | -1447    | 6,750   | -11,558    | 9,189     |
| Excluded based on Exclusion # 11.2 - Intraocular Bleeding                                                                                                                                                                                                                                                                                     | 0        | 4,660   | 0        | 6,750   | 0          | 9,189     |
| Excluded based on Exclusion # 11.3 - Gastrointestinal Bleeding                                                                                                                                                                                                                                                                                | -12      | 4,648   | -52      | 6,698   | -78        | 9,111     |

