## 10. Final Power Assessment

Date conducted: 12/16/20

- Re-calculate power in the appropriate excel table, using the revised number of matched patients from the PS-match in Section 9. All other parameters in the table should be the same as in Section 8.
  - Pooled

Effectiveness research with Real World Data to support FDA's regulatory decision making

| Non-inferiority Analysis |             |
|---------------------------------|-------------|
| Number of patients matched      | 7,140       |
| Reference                       | 3,570       |
| Exposed                         | 3,570       |
| Risk per 1,000 patients         | 13.74       |
| HR from RCT                     | 0.84        |
| Alpha (2-sided)                 | 0.05        |
| Non-inferiority margin          | 1.8         |
|                                 |             |
| Number of events expected       | 98.1036     |
| Power                           | 0.965194245 |

- Optum

| Non-inferiority Analysis |             |
|---------------------------------|-------------|
| Number of patients matched      | 980         |
| Reference                       | 490         |
| Exposed                         | 490         |
| Risk per 1,000 patients         | 12.93       |
| HR from RCT                     | 0.84        |
| Alpha (2-sided)                 | 0.05        |
| Non-inferiority margin          | 1.8         |
|                                 |             |
| Number of events expected       | 12.6714     |
| Power                           | 0.273097221 |

○ Marketscan

| Non-inferiority Analysis |             |
|---------------------------------|-------------|
| Number of patients matched      | 2,762       |
| Reference                       | 1,381       |
| Exposed                         | 1,381       |
| Risk per 1,000 patients         | 13.13       |
| Assumed HR from RCT             | 0.84        |
| Alpha (2-sided)                 | 0.05        |
| Non-inferiority margin          | 1.8         |
|                                 |             |
| Number of events expected       | 36.26506    |
| Power                           | 0.631133873 |

o Medicare

| Non-inferiority Analysis   |             |
|----------------------------|-------------|
| Number of patients matched | 3,398       |
| Reference                  | 1,699       |
| Exposed                    | 1,699       |
| Risk per 1,000 patients    | 14.66       |

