| 
Subjects with an indication, other than VTE, intended for long-term treatment with a VKA such as:
                                                                                            | 
N/A
                                                                                                                                                                                                                                                                                                                                                                                                            |                                                                                                                                                                                       |  |
| 
Mechanical valve
                                                                                                                                                                             | 
Measured 180 days prior to and including the drug initiation in any diagnosis position and in an inpatient or outpatient care setting
 
Mechanical valve
ICD-9 Dx: V43.3x
ICD-10 Dx: Z95.2x, Z95.3x, Z95.4x
ICD-9 Px: 35.0x, 35.2x, 35.3x
ICD-10 Px: O2RGxxx, O2RFxxx, O2RHxxx, O2RJxxx, O2QGxxx, O2QFxxx, O2QHxxx, O2QJxxx
                                                        |                                                                                                                                                                                       |  |
| 
Atrial fibrillation or atrial flutter with moderate to high risk of systemic thromboembolism. Subjects with atrial fibrillation that appears to be associated with acute PE may participate.
 | 
N/A
                                                                                                                                                                                                                                                                                                                                                                                                            |                                                                                                                                                                                       |  |

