| Atrial fibrillation; n (%)                                                        | 36 (7.3%)            | 36 (7.3%)           | 0.00      | 90 (6.5%)            | 84 (6.1%)           | 0.02      | 178 (10.5%)          | 180 (10.6%)         | 0.00      | 304 (8.5%)           | 300 (8.4%)          | 0.00      |
| Other cardiac dysrhythmia; n (%)                                                  | 90 (18.4%)           | 90 (18.4%)          | 0.00      | 241 (17.5%)          | 234 (16.9%)         | 0.02      | 365 (21.5%)          | 379 (22.3%)         | -0.02     | 696 (19.5%)          | 703 (19.7%)         | -0.01     |
| Cardiac conduction disorders; n (%)                                               | 28 (5.7%)            | 28 (5.7%)           | 0.00      | 87 (6.3%)            | 68 (4.9%)           | 0.06      | 126 (7.4%)           | 127 (7.5%)          | 0.00      | 241 (6.8%)           | 223 (6.2%)          | 0.02      |
| Other CVD; n (%)                                                                  | 137 (28.0%)          | 132 (26.9%)         | 0.02      | 332 (24.0%)          | 359 (26.0%)         | -0.05     | 420 (24.7%)          | 450 (26.5%)         | -0.04     | 889 (24.9%)          | 941 (26.4%)         | -0.03     |
| Diabetes-related complications                                                    |                      |                     |           |                      |                     |           |                      |                     |           |                      |                     |           |
| Occurrence of Diabetic Neuropathy v2                                              |                      |                     |           |                      |                     |           |                      |                     |           |                      |                     |           |
| Copy; n (%)                                                                       | 18 (3.7%)            | 24 (4.9%)           | -0.06     | 26 (1.9%)            | 25 (1.8%)           | 0.01      | 100 (5.9%)           | 99 (5.8%)           | 0.00      | 144 (4.0%)           | 148 (4.1%)          | -0.01     |

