| H2 receptor antagonist; n (%)                                              | 15 (3.1%)     | 21 (4.3%)   | -0.06       | 47 (3.4%)     | 49 (3.5%)     | -0.01   | 128 (7.5%)    | 139 (8.2%)    | -0.03       | 190 (5.3%)    | 209 (5.9%)    | -0.03   |
| Vitamin K therapy; n (%)                                                   | 0 (0.0%)      | 0 (0.0%)    | #DIV/0!     | 0 (0.0%)      | 0 (0.0%)      | #DIV/0! | 0 (0.0%)      | 0 (0.0%)      | #DIV/0!     | 0 (0.0%)      | 0 (0.0%)      | #DIV/0! |
| Number of INR (prothrombin) tests ordered                                  |               |             |             |               |               |         |               |               |             |               |               |         |
| ...mean (sd)                                                               | 0.80 (1.89)   | 0.53 (1.24) | 0.17        | 0.68 (1.73)   | 0.50 (1.11)   | 0.12    | 0.51 (1.10)   | 0.49 (1.06)   | 0.02        | 0.62 (1.49)   | 0.50 (1.11)   | 0.00    |
| Treating prescriber - Cardiologist; n (%)                                  | 299 (61.0%)   | 313 (63.9%) | -0.06       | 871 (63.1%)   | 868 (62.9%)   | 0.00    | 880 (51.8%)   | 902 (53.1%)   | -0.03       | 2050 (57.4%)  | 2083 (58.3%)  | -0.02   |
| Treating prescriber - Primary Care Physician                               | 415 (84.7%)   | 407 (83.1%) | 0.04        | 600 (43.4%)   | 636 (46.3%)   | -0.05   | 642 (37.8%)   | 637 (37.5%)   | 0.01        | 1657 (46.4%)  | 1680 (47.1%)  | -0.01   |
| Treating prescriber - Other; n (%)                                         | 474 (96.7%)   | 476 (97.1%) | -0.02       | 1,287 (93.2%) | 1,288 (93.3%) | 0.00    | 1,613 (94.9%) | 1,617 (95.2%) | -0.01       | 3374 (94.5%)  | 3381 (94.7%)  | -0.01   |
| Alpha blockers; n (%)                                                      | 30 (6.1%)     | 21 (4.3%)   | 0.08        | 54 (3.9%)     | 56 (4.1%)     | -0.01   | 123 (7.2%)    | 125 (7.4%)    | -0.01       | 207 (5.8%)    | 202 (5.7%)    | 0.00    |
| CHA2DS2 VASc score, 180 days, V                                            |               |             |             |               |               |         |               |               |             |               |               |         |

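### The trial's exclusion of atrial fibrillation/flutter at moderate to high thromboembolic risk is marked N/A although AF and CHA2DS2-VASc are measured; up to 604 of 7,140 matched patients (8.5%) carry an AF code

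*Combined protocol and SAP*

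**What the plan says.** Section 5.2.2 sets the standard: "Inclusion and exclusion criteria were adapted from the trial as closely as possible". Appendix A reproduces the trial's parent exclusion, "Subjects with an indication, other than VTE, intended for long-term treatment with a VKA such as", and gives two examples under it.

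- Mechanical valve has a code list and a 180-day window, and Section 5.3 applies it in a combined row ("based on Exclusion # 10A - Mechanical Valve").
- The other example is "Atrial fibrillation or atrial flutter with moderate to high risk of systemic thromboembolism". Its implementation cell reads N/A, with no reason given. The same cell carries an exception: "Subjects with atrial fibrillation that appears to be associated with acute PE may participate".

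No row of the Section 5.3 flowchart removes patients for AF or flutter. Appendix B nevertheless reports an AF variable (the row beginning "Atrial fibrillation; n") before and after matching, and a stroke-risk score ("CHA2DS2 VASc score, 180 days, V").

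**The concern.** The study is judged by how closely it reproduces the trial's 0.84 (Section 1.6) and 0.31 (Section 1.5). Those estimates come from a population without patients who had another standing reason for long-term anticoagulation. In the claims cohort, a PE or DVT code in any position from an inpatient or ED setting, up to 180 days before drug start, is enough to qualify. Nothing ties the prescription to that event. A patient with established AF who starts warfarin or apixaban for AF, and who had such a code some months earlier, would enter as a treated acute-VTE patient.

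Such patients may also stay on treatment longer than a VTE course. Section 6.3.2 gives the primary as-treated analysis no maximum follow-up; only the ITT analysis is capped, at 365 days.

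Imperfect measurement does not by itself explain the N/A. Appendix A accepts proxies for other criteria that claims cannot capture directly: HAS-BLED of 3 or more for bleeding risk, CCI of 10 or more for short life expectancy, and malignant-hypertension or hypertensive-crisis codes for blood pressure.

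**Working it through.** **Count of coded AF, matched cohort (Appendix B, PS-matched table)**

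| Database | Warfarin | Apixaban | Total / matched N | % |
|---|---|---|---|---|
| Optum | 36 | 36 | 72 / 980 | 7.3 |
| MarketScan | 90 | 84 | 174 / 2,762 | 6.3 |
| Medicare | 178 | 180 | 358 / 3,398 | 10.5 |
| Pooled | 304 | 300 | 604 / 7,140 | 8.5 |

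The printed pooled standardized difference is 0.00. Before matching the counts are 738 of 8,919 and 729 of 10,063, that is 1,467 / 18,982 = 7.7%.

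**What the count does not show.** The trial's criterion has a risk qualifier and an exception for AF linked to the PE. The table gives neither stroke risk nor AF onset relative to the PE for the AF patients. CHA2DS2-VASc appears only for all matched patients (pooled means 1.42 and 1.43). Section 6.2 defines the baseline period as 180 days up to and including the index date, so AF first coded during the PE admission can be counted. PE is present in 3,563 and 3,566 of 3,570 patients per arm, so the exception could apply to nearly anyone. The number meeting the trial's exclusion therefore lies anywhere from 0 to 604 of the coded patients.

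**The plan's power figure reproduced.** Inputs from Section 10, pooled: N = 7,140; risk 13.74 per 1,000; HR 0.84; two-sided alpha 0.05; "Non-inferiority margin" 1.8.

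- Events: D = 7,140 × 13.74 / 1,000 = 98.1036, as stated.
- Power = Φ(√(D/4) × ln(1.8/0.84) − 1.96) = 0.9652. The plan states 0.965194245.
- The same formula returns the stated values for Optum (0.2731), MarketScan (0.6311) and Medicare (0.7672).

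**Power after removal**, holding the risk at 13.74 per 1,000 (an assumption):

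| Removed | N left | Events | Power |
|---|---|---|---|
| 302 (half of the coded patients, an assumed share) | 6,838 | 94.0 | 0.959 |
| 604 (all coded patients, as individuals) | 6,536 | 89.8 | 0.951 |
| 1,208 (every affected pair, none containing two AF patients) | 5,932 | 81.5 | 0.931 |

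The last row is the worst case without re-matching: 2 × 604 = 1,208, or 16.9% of 7,140.

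**The case against.** A reader might infer that all 604 patients have a competing reason for anticoagulation. The documents do not support that: the trial excluded only AF/flutter at moderate to high risk and admitted AF that appeared associated with the PE, so 604 is a ceiling among coded patients. A reader might also infer that AF biases the hazard ratio. That is not shown either. AF is balanced after matching, and a shift in the hazard ratio would need AF to modify the treatment effect, for which the documents offer no evidence.

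Other points on that side carry weight:

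- N/A does not always mean unmeasurable in Appendix A. It is also used where a criterion is handled under another row, as for contraception and liver enzymes. The AF row carries no such cross-reference.
- Existing rules narrow the scenario. The qualifying code must be inpatient or ED, prior apixaban or warfarin use in 180 days is excluded, and other NOAC users are removed. In the matched arms 80.3% and 81.1% had a hospitalization in the prior 30 days. That leaves about a fifth without a recent admission, although a recent ED visit could also qualify them.
- The absence of an as-treated cap affects everyone. Median follow-up by database and arm is 72 to 100 days, with upper quartiles of 155 to 195, and nothing shows that AF patients form the long tail.
- Excluding on diagnosis alone would remove low-risk AF patients whom the trial admitted.

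These points limit the size and certainty of the concern. They do not explain why one example is coded and the other left blank.

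**Conclusion.** The point holds as a gap in fidelity to the trial population and indication. A named trial exclusion is left unapplied without a stated reason, although the diagnosis and a stroke-risk score are both in the dataset and the companion criterion is implemented. At most 604 of 7,140 matched patients (8.5%) with coded AF are affected, and the true share is unknown. Whether the AF variable includes flutter is not stated, so patients with flutter alone may lie outside that count.

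No confounding by measured AF, direction of bias or effect on the hazard ratio is demonstrated. The power figures rest on the plan's formula and on an unchanged event risk. On that basis, stated power stays above 0.90 even if every affected pair is lost without replacement.

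**What to change.** Before the comparative analyses in Section 13:

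1. Replace N/A with a claims proxy: AF or flutter coded in the 180 days before the start of the qualifying VTE encounter. Keep patients whose AF is first coded on that encounter, to mirror the trial's exception.
2. Either combine the diagnosis with the CHA2DS2-VASc already measured, to reflect the risk qualifier, or state that a diagnosis-only rule is stricter than the trial's. If the score is used, its cut-off must be pre-specified, since the documents give none.
3. Confirm that the AF variable includes flutter, and extend it if it does not.
4. Add the flowchart row, re-run the match and restate Sections 9 and 10.

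At minimum, pre-specify a sensitivity analysis excluding prior AF and give the reason for N/A.

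The work is a date condition on an existing variable, possibly extended for flutter, and a re-run of the match. The price in power is bounded by the removal scenarios worked above: about 0.951 if all coded patients go, and about 0.931 if all affected pairs go. The actual loss after re-matching cannot be computed from the documents and should be reported when the match is repeated.

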# Appendix A

|                                                             |                                                                                                                                                                                                                                                                                                                                                                                                                                                                                                                                                                                                                                                                                                                                                                                                                            |  |  |
|-------------------------------------------------------------|----------------------------------------------------------------------------------------------------------------------------------------------------------------------------------------------------------------------------------------------------------------------------------------------------------------------------------------------------------------------------------------------------------------------------------------------------------------------------------------------------------------------------------------------------------------------------------------------------------------------------------------------------------------------------------------------------------------------------------------------------------------------------------------------------------------------------|--|--|
|                                                             | 
Measured 180 days prior to and including day of drug initiation in any diagnosis position and in an inpatient care setting
 
Gastrointestinal bleeding:
 
ICD-9 Dx:
531.0x gastric ulcer w/ hemorrhage,
531.2x gastric ulcer w/ hemorrhage and perforation
531.4x
531.6x chronic / unspecified ulcer w/ hemorrhage
532.0x, 532.2x, 532.4x, 532.6x, 533.0x, 533.2x, 533.4x, 533.6x,
534.0x, 534.2x, 534.4x, 534.6x, 562.0x, 562.1x, 568.8x, 569.3x, 569.8x
578.x Gastrointestinal hemorrhage
 
ICD-10 Dx:
K25.0x, K25.2x, K25.6x, K26.0x, K26.2x, K26.4x, K26.6x, K27.0x, K27.2x, K27.4x, K27.6x,
K28.0x, K28.2x, K28.4x, K28.6x, K55.21, K57.xx, K62.5x, K63.1x, K63.81, K66.1x, K92.0x,
K92.1x, K92.2x
 
ICD-9 Px: 44.43
ICD-10 Px: 0W3PBZZ
 |  |  |
| • 2 months                                                  |                                                                                                                                                                                                                                                                                                                                                                                                                                                                                                                                                                                                                                                                                                                                                                                                                            |  |  |
| Head trauma or other major trauma                           | 
Measured 60 days prior to and including the day of drug initiation in any diagnosis position and in an inpatient or outpatient care setting
 
See 'Major Trauma' sheet for codes
                                                                                                                                                                                                                                                                                                                                                                                                                                                                                                                                                                                                                               |  |  |
| Major surgery                                               | 
Measured 60 days prior to and including the day of drug initiation in any diagnosis position and in an inpatient or outpatient care setting
 
Major surgery selected from codes range 35.x- 84.x
                                                                                                                                                                                                                                                                                                                                                                                                                                                                                                                                                                                                               |  |  |
| • 1 week                                                    |                                                                                                                                                                                                                                                                                                                                                                                                                                                                                                                                                                                                                                                                                                                                                                                                                            |  |  |
| - Ischemic stroke                                           | 
Measured 7 days prior to and including the day of drug initiation in any diagnosis position and in an inpatient care setting
 
Ischemic stroke:
 
ICD-9 Dx: 433.x, 434. x, 436.xx
                                                                                                                                                                                                                                                                                                                                                                                                                                                                                                                                                                                                                  |  |  |
| - Neurosurgery                                              | 
Measured 7 days prior to and including the day of drug initiation in any diagnosis position and in an inpatient care setting
 
Neurosurgery:
 
ICD-9 Px:
01.xx, 02.xx, 03.xx, 04.xx, 05.xx
ICD-10 Px:
00xxxx
                                                                                                                                                                                                                                                                                                                                                                                                                                                                                                                                                                           |  |  |
| • Time of randomization                                     |                                                                                                                                                                                                                                                                                                                                                                                                                                                                                                                                                                                                                                                                                                                                                                                                                            |  |  |
| - Gross hematuria                                           | 
Measured 1 day prior to and including the day of drug initiation in any diagnosis position in an inpatient or outpatient care setting
 
Gross hematuria:
 
ICD-9 Dx: 599.71 (not 599.7x)
ICD-10 Dx: R31.0
                                                                                                                                                                                                                                                                                                                                                                                                                                                                                                                                                                                      |  |  |
| - Evidence of poor healing of a major wound or major trauma | 
Measured 1 day prior and including the day of drug initiation in any diagnosis position in an inpatient or outpatient care setting
 
Non-healing surgical wound
 
ICD-9 Dx: 998.33
ICD-10 Dx: T81.33XA
                                                                                                                                                                                                                                                                                                                                                                                                                                                                                                                                                                                         |  |  |
| - Planned major surgery                                     | N/A                                                                                                                                                                                                                                                                                                                                                                                                                                                                                                                                                                                                                                                                                                                                                                                                                        |  |  |

